15.0 Risks to Subjects*

We believe that there is minimal risk for being in this study.

It is possible that the subject might feel motion sickness using the virtual reality goggle. They might also experience other virtual reality side effects, which can include but are not limited to, blurry vision, eye strain, headaches, dizziness, fatigue, or nausea. The subject has the right to terminate using the virtual reality goggle any time during the study if there is any discomfort arising from using the virtual reality goggle. The risk of motion sickness will be minimized by allowing subjects to terminate use of the VR intervention at any time during the study.

Although we will take every precaution including secure data storage on password-protected computers and REDCap, there is a small chance of loss of confidentiality of study information. The risks related to patient confidentiality will be minimized by creating a separate link file for patient study ID and the MRN. The study ID will be used on the questionnaires. Patients' medical data will be reviewed and abstracted by trained researchers. All data will be stored on a secure server at NCH. The Patient ID-Participant ID link file will be stored in a separate location on the server from other study data for an additional layer of security and confidentiality.

16.0 Potential Benefits to Subjects*

There are no known direct physical, psychological or social benefits immediately for the subject, although it is possible that the subject might have fun playing the virtual reality games and he/she might experience improved cognitive rehabilitation with use of the virtual reality tools.

In general, we anticipate that this study will provide critical data to improve rehabilitation methods available for pediatric TBI patients, and potentially help future patients to further improve TBI rehabilitation.

17.0 Data Management* and Confidentiality

17.1 Describe the data analysis plan, including any statistical procedures or power analysis.

To examine the research paradigm (Aim 1), we will compute average number of children screened and enrolled per month, proportion of eligible children who enroll, treatment-specific retention rates, proportion of children who adhere to assigned condition, proportion of planned measures that are completed, and average duration of completing each measurement. To examine the feasibility and safety of the VICT program (Aim 2), the total number of AEs/SAEs, mean simulator sickness scores, and mean Borg exertion scores will be computed and compared between the intervention and control group using independent samples t-tests. Additionally, open-end feedback from children, parents, and clinicians on optimizing the VR games and best practices in protocol implementation will be synthesized and submitted to the VR development team for improvement. Finally, to explore the preliminary efficacy of the VICT program (Aim 2), difference scores from baseline to post-intervention and baseline to follow-up of the composite NIH Toolbox score, TBI-QOL, and Conners CPT 3 will be compared between the intervention group and the control group using analysis of covariance (ANCOVA) controlling for baseline scores. BRIEF2, CBCL-APS, and PedsQL (parent/child) scores at follow-up will be compared between the two groups using ANCOVA controlling for baseline scores. Cohen's d for core EFs changes will be computed as the preliminary intervention effect size. Finally, dosage effect will be evaluated within regression analyses, with dosage (0 for controls, cumulative hours of VICT training for intervention group) as the primary predictor and post-intervention NIH Toolbox scores as the outcome variable.

17.2 Describe the steps that will be taken to secure the data (e.g., training, authorization of access, password protection, encryption, physical controls, certificates of confidentiality, and separation of identifiers and data) during storage, use, and transmission.

All data will be independently entered into a computerized database by trained research staff and verified by the PI. All data files will be maintained in the central electronic database system, REDCap (Research Electronic Data Capture), which is securely stored at the Research Institute at NCH. Each participant will be assigned a unique Study ID number. The master file that links the participants' names to their Study IDs will be maintained only in a password

protected file in a password-protected computer at the Research Institute at Nationwide Children's Hospital. All measurement and randomization procedures will only use Study IDs to record data without participants' names attached.

17.3 Describe any procedures that will be used for quality control of collected data.

Once data are collected and entered into electronic databases by one researcher, another researcher or the PI will independently verify the records to ensure accuracy.

17.4 Describe how data or specimens will be handle study-wide:

- *What information will be included in that data or associated with the specimens?*

The data to be collected include: Age, gender, race, injury severity scores, including Glasgow Coma Scale score and Rancho Scale level, gaming performance in the virtual program, and standard neuropsychological testing results. Demographic and medical variables listed above will be collected via patients' medical records. We will also include the amount of time spent in each rehab therapy using the Rehabilitation Provision of Services flow sheet in EPIC. Performance in games will be automatically recorded by the virtual reality computer program. Cognitive variables will be collected via standard neuropsychological tests.

A Microsoft Excel spreadsheet will be created for use by the study recruiters in order to keep track of patients that fit the inclusion criteria and are recruited, and also of patients who meet exclusion criteria and are not recruited. The spreadsheet will include the following variables: MRN, patient name, gender, age, guardian name(s), telephone number(s), email address(es), recruited (Y/N), study ID number, study group (Intervention or Control), dates of VR therapy, times of VR therapy, and reason for exclusion (for patients that are not recruited). The rationale behind the eligibility spreadsheet is to track how many pediatric TBI patients are treated, and of those, how many are willing to participate in our study. This spreadsheet will be helpful for research project planning in order to guide our enrollment number prediction and also to reach out to families after discharge in order to schedule their follow-up research appointments. This password-protected spreadsheet will be kept in a secure file folder on password protected computers in the Research Institute at Nationwide Children's Hospital. Only researchers on the IRB will have access to the secure folder where the file is located.

PROTOCOL TITLE: Virtual Reality-based Rehabilitation for Children with Traumatic Brain Injuries

- *Where and how data or specimens will be stored?*

Data will be stored either on paper forms or electronically on password-protected computers and/or REDCap databases

- *How long the data or specimens will be stored?*

Data will be stored up to 10 years after the completion of the study.

- *Who will have access to the data or specimens?*

Only personnel listed on the IRB application will have access to the data.

- *Who is responsible for receipt or transmission of the data or specimens?*

Personnel listed on the IRB application will be responsible for receipt or transmission of the data.

- *How data or specimens will be transported?*

Currently there is no need to transport data.

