4.0 Study Endpoints

4.1 Describe the primary and secondary study endpoints.

The primary study endpoint is the protocol feasibility (defined as protocol completion rate and subjective VR experience ratings) and safety (see section 4.2) of the VICT program. The second study endpoint is the preliminary efficacy of the VICT program, defined as the changes in NIH Toolbox Composite Scores before and after the intervention.

4.2 Describe any primary or secondary safety endpoints.

The primary safety endpoint is the number of adverse events. The secondary endpoint is the scores on participants' simulator sickness and exertion.

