5.0 Study Intervention/Investigational Agent

5.1 Description:

The hardware of the VICT program consists of a fully-immersive High Tech Computer (HTC) VIVE™ VR viewer (OLED display with 2160×1200 resolution, 90Hz refresh rate, and 110 degrees of field of view) powered by a high-performance laptop (Dell Alienware™ 17), a pair of surround sound headphones reworked to integrate with the VR viewer, and a wireless one-hand controller for the child to interact with the virtual environment using gestures. Furthermore, to avoid the burden of the equipment's weight on a child's head, we created a special mechanical arm to suspend the VR viewer in front of a child's eyes with adjustable headphone positions. With the system securely fixed on a wheeled workstation, a child can operate the program by reclining on the bed/wheelchair in his/her own patient room. To ensure the hygiene, each child will use a new facial pad for the viewer and a pair of new earphone covers. All parts of the equipment will be sanitized with germicidal wipes after each use.

For the software, the Windows 10-based VICT program invites children to rescue an animated character named "Lubdub" from a castle. The program consists of three challenging and child-friendly tasks that correspond to the three core EFs. During the game, children need to (1) direct a group of sentinels away from the castle gates (VR Task #1, adapted from the Spatial Stroop Task to train Inhibitory

Control), (2) successfully open a series of castle gates by replicating the cryptography sequence of items surrounding each gate in forward/backward order (VR Task #2, adapted from the Visual Working Memory Task to train Working Memory), and finally (3) rescue Lubdub inside the castle by strategically matching patterns between the Lubdub and the four surrounding guards (VR Task #3, adapted from the Wisconsin Card Sorting Task to train Cognitive Flexibility). A tutorial mode preceding the training lets children learn how to interact with VR. In the training mode, children will complete each task starting at the easiest level and gradually moving to more difficult levels as easier levels are mastered. Each training session consists of 10-30 trials per task, taking about 15 minutes in total. Children will receive visual/audio feedback to learn and optimize their performance.

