6.0 Procedures Involved*

The procedure involved for the study is described in detail below:

1) Baseline assessment. All approximately 30 children will complete the NIH Toolbox Cognition Battery tests, CPT 3, Virtual Reality Assessment, and the TBI-QOL Short Form prior to the randomization sequence. Both the assessor and the child will be unaware of group assignment at this point. Additionally, data regarding baseline measurement including proportion of planned baseline measures that are completed and the duration of each assessment will be documented.

2) Intervention. Following the baseline assessment, the approximately 30 children will be randomly assigned to one of the following two groups: intervention group (VICT training) or control group (a comparable VR game without cognitive training). The random allocation sequence will be generated using a SAS-based randomization program with 1:1 allocation ratio and random block sizes of 2 and 4. Both groups will first be provided a tutorial to be familiar with the VR environment. The length of time for either intervention game will be a minimum of 15 minutes of total play. If they are in the hospital, they will play approximately 15 minutes per day during their stay. If they have already been discharged from the hospital, the length of time is a minimum of 15 minutes of total play but can be more spread across their choice of days. Trained researchers who generate the randomization sequence and implement the VR will not participate in any subsequent outcome assessment. Note that although the length of training will vary across children depending on their length of stay or if they have been discharged, this arrangement has unique advantages over a fixed length of training in that: a) it provides consistency with standard therapies children are scheduled to receive, ensuring intervention to meet children's medical needs; and b) it ensures consistent timing and sufficient retention rates for future assessment.

Additionally, AEs and SAEs will be monitored in real-time throughout the intervention. Quantitative user feedback such as sickness, fatigue, and time estimates will be measured at the end of both the first and the last VR session. The

PROTOCOL TITLE: Virtual Reality-based Rehabilitation for Children with Traumatic Brain Injuries

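### The only inferential safety analysis is a t-test against another VR game; no count of affected children and no confidence interval is planned

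*Combined protocol and SAP*

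**What the plan says.** Section 4.1 states: "The primary study endpoint is the protocol feasibility (defined as protocol completion rate and subjective VR experience ratings) and safety (see section 4.2"). Section 4.2 adds: "The primary safety endpoint is the number of adverse events". Simulator sickness and exertion scores are the secondary safety measures. Sections 1.0 and 2.1 instead place safety under the secondary objective, as something to explore, and Section 2.2 states no hypotheses.

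The quantitative safety analysis is one sentence in Section 17.1: "the total number of AEs/SAEs, mean simulator sickness scores, and mean Borg exertion scores will be computed and compared". The method follows: these are "compared between the intervention and control group using independent samples t-tests". No other section plans a proportion of children with an AE, or an interval for any safety measure.

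The comparator in Section 6.0 is a "control group (a comparable VR game without cognitive training"). Section 15.0 attributes the expected side effects to VR use in general, not to the VICT content.

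On timing, Section 6.0 says that user feedback, including sickness and fatigue, "will be measured at the end of both the first and the last VR session". It also says: "The length of time for either intervention game will be a minimum of 15 minutes of total play". Section 5.1 describes one training session as "taking about 15 minutes in total". Section 9.1 sets no upper limit on training time.

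Section 14.0 has a pause rule that applies when the share of participants with procedure-related SAEs passes 20%.

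**The concern.** The question for a first study of this kind is what share of children exposed to VR had an adverse event, and how precisely that share is known. Section 17.1 does not commit to answering it, for four reasons.

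- Both arms are in VR, so any harm from the headset or from immersion drops out of the between-arm contrast.
- The AE total is one figure per arm. A t-test needs one value per child, and the plan does not define it. A total also does not separate a few children with many events from many children with one event each.
- No interval is planned, so few or no events would be reported without showing what rate they leave open.
- Sickness is scored after the first and the last session, and Section 17.1 does not say which score is compared. With a session of about 15 minutes and a minimum total of 15 minutes, the two could be the same session for some children.

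At stake is what a later study can take from this one on safety.

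**Working it through.** The documents give no AE rate, SD or alpha, so there is no planned figure to reproduce. The AE counts below are illustrations, not estimates.

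**Inputs.** About 30 children (Sections 1.0 and 12.1) and 1:1 allocation (Section 6.0), hence 15 per arm by assumption. Two-sided 5% level and 95% intervals, also assumed.

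**1. Shared harm cancels.** Take one AE per affected child, so each child scores 0 or 1. The t statistic is the difference in means divided by its standard error.
- 1/15 v 1/15: difference 0, t = 0, p = 1.00. Pooled 2/30 = 6.7%, Clopper-Pearson 95% CI 0.8% to 22.1%.
- 6/15 v 6/15: difference 0, t = 0, p = 1.00. Pooled 12/30 = 40%, CI 22.7% to 59.4%.

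The test result is the same and the safety picture is not.

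**2. A total hides the number of children.** Take 15 AEs among 30 children, a mean of 15/30 = 0.50 per child. SD = √[(Σx² − 30 × 0.50²)/29], and the interval is mean ± 2.045 × SD/√30.

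| | 3 children, 5 AEs each | 15 children, 1 AE each |
|---|---|---|
| Total AEs | 15 | 15 |
| SD per child | √[(75 − 7.5)/29] = 1.53 | √[(15 − 7.5)/29] = 0.51 |
| 95% CI of mean, t-based | −0.07 to 1.07 | 0.31 to 0.69 |
| 95% CI of mean, percentile bootstrap over children | 0 to 1.17 | 0.33 to 0.67 |
| Children affected (exact 95% CI) | 10% (2.1% to 26.5%) | 50% (31.3% to 68.7%) |

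The bootstrap limits follow from the binomial number K of affected children in a resample. In the first column K ~ Bin(30, 0.1), with 2.5% and 97.5% points 0 and 7, so the limits are 0 and 7 × 5/30 = 1.17. In the second K ~ Bin(30, 0.5), with points 10 and 20, so 10/30 and 20/30. An exact Poisson interval, which ignores clustering, is 0.28 to 0.82 for both columns.

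**3. The test itself depends on the undefined unit.** Suppose 6 AEs on VICT against 1 on control, 15 per arm, with the t-test on per-child counts. If all six occur in one child, p = 0.42. If they occur in six children, p = 0.03. The totals are identical.

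**4. What zero events would leave open.** The upper limit is 1 − 0.025^(1/n).
- n = 30: 1 − 0.025^(1/30) = 11.6%.
- n = 15: 1 − 0.025^(1/15) = 21.8%.

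**5. Precision of the scores, in SD units.**
- Pooled mean: 2.045/√30 = ±0.37 SD.
- Mean per arm: 2.145/√15 = ±0.55 SD.
- Difference between arms: 2.048 × √(2/15) = ±0.75 SD.

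The t-test has 80% power only for a difference of about 1.06 SD, and 26% power at 0.5 SD.

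**The case against.** - **Status of safety.** Sections 1.0 and 2.1 make safety a secondary, exploratory objective, and Section 2.2 tests no hypotheses. This stands, and it lowers the weight of the point. It also favours estimation: where nothing is to be tested, an estimate with an interval is the natural output.
- **Absolute levels are visible.** A reader might infer that the plan would leave shared harm unseen. The documents do not support that. Totals and means are to be computed, AEs are monitored as they occur, and children are interviewed about their experience. Two AEs and twelve AEs among 30 children would look different. What is missing is the number of children behind a total, and its precision.
- **Reading of a null result.** A reader might infer that the investigators will take a non-significant t-test as evidence of safety. No section says so. The point is only that such a result would carry little information at this size.
- **Per-child tracking.** The Section 14.0 rule does require counting children, so it would be wrong to say that no per-child figure is ever needed. It covers procedure-related SAEs only, and it serves trial conduct, not reporting.
- **Nothing is lost.** Incidence could be derived later from the children's records, and interval width comes from the sample size, not from the wording. Both are true. The gain is a commitment made in advance for a component of the primary endpoint.

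**Conclusion.** The point holds as a cheap improvement to the analysis of a primary-endpoint component. The planned t-test compares two VR-exposed arms and cannot show harm that both share. The AE total does not give the number of children affected, and no safety measure has an interval. With 15 per arm, the same p = 1.00 is compatible with 6.7% or 40% of children affected, and the same total of 15 AEs with 10% or 50%.

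This rests on assumed arm sizes of 15 and on invented event counts. It does not show that safety data will be lost or that the investigators will draw a wrong conclusion. That the first and last sessions coincide is possible from the stated times, but no section says how often it would occur.

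One limit applies under any wording. Without an unexposed comparison, pooled incidence describes VR-exposed children and cannot be attributed to VR.

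**What to change.** Reword the safety sentence in Section 17.1 as follows.

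1. Keep the AE count of Section 4.2 as the primary safety measure. Report the total and the mean count per child, by arm and pooled, with a 95% interval that allows for clustering within children, for example a bootstrap over children. With no events the bootstrap collapses to zero width, so rely then on the exact limit in item 2. With few affected children it is coarse: with 3 of 30, a resample contains none of them with probability 0.9^30 = 4.2%.
2. Beside it, report the number and proportion of children with at least one AE and at least one SAE, by arm and over all VR-exposed children, with Clopper-Pearson 95% CIs. If this proportion is to be the main measure, amend Section 4.2 to say so.
3. Report mean sickness and exertion scores with 95% CIs, by arm and pooled, separately for the first and last session. State how many children contributed and how many had only one session.
4. Base the safety conclusion on the estimates. Give the between-arm difference with its CI descriptively, in place of the t-test, and state that pooled incidence cannot be attributed to VR.
5. Because play time has no upper limit, add AEs per VR hour as supportive, at least in the VICT arm, where Section 17.1 already plans cumulative hours. The recruitment tracker in Section 17.4 lists times of VR therapy, but it is unclear whether this means duration.

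The cost is wording and a few lines of code, with no new AE, sickness or exertion data. The downside is slightly more analysis and wide intervals at about 30 children.

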9.0 Study Timelines*

9.1 Describe:

- **The duration of an individual subject's participation in the study.**
 - An individual subject's participation includes up to three assessment visits (pre-intervention visit, post-intervention visit, and follow-up visit) as well as the intervention training. The assessment visits last approximately 60 minutes per visit. The intervention training will last a minimal of 15 minutes. Since part of the purpose of the study is to explore the dose effect of the intervention, we do not set an upper limit of the intervention length, which could depend on patient's preference and patient's length of stay (if inpatient). We expect the total duration of subject's participation to last up to six months (depending on how far out the subject's follow-up appointment is scheduled upon completion of intervention).
- **The duration anticipated to enroll all study subjects.**
 - Approximately 24 months
- **The estimated date for the investigators to complete this study (complete primary analyses)**
 - August 31, 2021

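### Adverse event totals are compared between arms with no exposure denominator, although VR play has no upper limit, so an arm that plays less can look safer and the plan would not show it

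*Combined protocol and SAP*

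**What the plan says.** Section 4.2 defines the endpoint as a plain count: "The primary safety endpoint is the number of adverse events". Section 17.1 states that "the total number of AEs/SAEs, mean simulator sickness scores, and mean Borg exertion scores will be computed and compared", with the arms "compared between the intervention and control group using independent samples t-tests". No rate per session, per hour or per child-day is planned for adverse events.

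The counting window is the intervention itself. Section 6.0, item 2: "AEs and SAEs will be monitored in real-time throughout the intervention". That window is elastic. Section 6.0 sets a floor for both games: "The length of time for either intervention game will be a minimum of 15 minutes of total play". Section 9.1 sets no ceiling: "we do not set an upper limit of the intervention length, which could depend on patient's preference and patient's length of stay". Inpatients play about a quarter of an hour daily until discharge, and discharged children choose their own days. Section 15.0 lets a child stop using the headset at any time for discomfort.

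Dose appears once in section 17.1, in the efficacy regression on NIH Toolbox scores. Controls are coded 0 there, so that analysis carries no information on VR exposure in the control arm. The raw material for a denominator does exist: the tracking spreadsheet in section 17.4 holds "dates of VR therapy, times of VR therapy".

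**The concern.** A count over a window of variable length mixes two things: how risky a session is, and how many sessions there were. Exposure can differ between arms in two ways. With about 15 children per arm, chance can leave one arm with longer stays. Preference and early stopping also act after randomisation and may depend on which game was assigned. A game that makes children unwell can shorten its own exposure and so hold down its own event count.

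Safety is part of the primary endpoint in section 4.1, and section 3.3 gives safety data as a reason the research matters. If totals are read as risk, two equally safe games can look different, or a real difference in tolerability can be masked. This does not depend on the t-test: any test on raw totals has the same weakness.

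**Working it through.** The plan states no event rate, session count, alpha or power, so there is no figure to reproduce. From the documents: about 30 children allocated 1:1, hence n = 15 per arm; a 15-minute minimum; no maximum. Everything else below is assumed: per-session risks, mean sessions, and two-sided 0.05. A t-test needs one count per child, which section 17.1 does not spell out; this too is assumed.

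**Identity.** Expected total per arm = n × risk per session × mean sessions. Hence ratio of totals = rate ratio × exposure ratio.

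- Equal risk 0.10, 8 vs 10 sessions: 15 × 0.10 × 8 = 12 against 15 × 0.10 × 10 = 15; ratio 0.80, true rate ratio 1.0.
- Equal risk 0.10, 5 vs 10: 7.5 against 15; ratio 0.50.
- Risk 0.20 vs 0.10, 8 vs 10: 24 against 15; ratio 1.60 = 2.0 × 0.8. Diluted, not reversed.
- Risk 0.20 vs 0.10, 5 vs 10: 15 against 15; ratio 1.00 = 2.0 × 0.5. This is exactly break-even.
- Risk 0.15 vs 0.10, 5 vs 10: 11.25 against 15; ratio 0.75. Reversed, because the exposure ratio of 2.0 exceeds the risk ratio of 1.5.

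**Early stopping.** Suppose 10 sessions are planned in each arm, each child stops after a first event, and risk is 0.20 vs 0.10. Each child then contributes at most one event, so the count ratio is (1 − 0.8^10)/(1 − 0.9^10) = 0.893/0.651 = 1.37, while the per-session rate ratio is 2.0. Again this is dilution without reversal.

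**Simulation.** 15 per arm, sessions = 1 + Poisson, same risk for every child within an arm:

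| Risk (less-played vs other arm) | Mean sessions | t-test on counts rejects | Less-played arm has equal or lower total |
|---|---|---|---|
| 0.10 vs 0.10 | 8 vs 10 | about 8% (false) | – |
| 0.10 vs 0.10 | 5 vs 10 | about 33% (false) | – |
| 0.02 vs 0.02 | 5 vs 10 | about 7–9% (false) | – |
| 0.20 vs 0.10 | 8 vs 10 | – | about 8% |
| 0.20 vs 0.10 | 5 vs 10 | about 5% | about 54% |

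**Chance imbalance.** Give both arms the same log-normal session distribution with mean 10. The larger arm mean exceeds the smaller by more than 1.25-fold (a gap of 10 vs 8) in about 21%, 40% and 52% of randomisations for a coefficient of variation of 0.5, 0.75 and 1.0. It exceeds 1.5-fold in about 2%, 13% and 25%. This does not raise the long-run error of the t-test (4.5% at equal risk, coefficient 0.75). It does mean that the totals in any one trial may reflect unequal play.

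**Which rate analysis.** Let risk vary between children (beta, mean 0.10, concentration 9, 4 or 2) with equal exposure. An exact conditional test that treats all sessions as independent then falsely rejects in roughly 12%, 21% and 30% of trials. The planned t-test stays at about 4–5%, and a rate ratio with child-level robust standard errors at about 5–8%.

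**The case against.** A reader might infer that the less-played arm will look safer even when it is riskier. The documents do not support that. Reversal is expected only when the exposure ratio exceeds the risk ratio, and at 8 vs 10 sessions with a doubled risk the totals still rank the arms correctly in about 92% of trials (100% − 8%).

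A reader might also infer that exposure will differ by arm. Nothing in the documents predicts this. Both arms share the same tutorial, minimum and inpatient schedule, the control is described as a comparable VR game, and randomisation balances length of stay in expectation. The two-fold gap behind the 33% and 54% figures is an illustration, and the 54% case sits at break-even by construction.

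Three further points have force. The study is exploratory and tests no hypotheses (section 2.2), so what is at stake is interpretation, not a confirmatory error rate. Events per child under the assigned programme is a legitimate measure of burden. Tolerability at equal exposure is partly covered, because sickness and fatigue are recorded after the first session for every child (section 6.0).

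These limit the size of the point without removing it. The plan neither ensures balanced exposure nor reports it, so burden and risk cannot be told apart.

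**Conclusion.** The point holds in conditional form. Sections 4.2 and 17.1 compare event totals over a window that lengthens with play, and no planned output would show whether the arms played equally. If they did not, the less-played arm can look safer than it is.

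Under an assumed equal risk of 0.10 per session, false rejection runs from about 8% (10 vs 8 sessions) to 33% (10 vs 5), and is about 7–9% at 10 vs 5 if the risk is 0.02. With risk 0.20 against 0.10, the riskier, less-played arm has an equal or lower total in about 8% to 54% of trials over the same range of exposure. These figures rest on assumed risks, session counts and constant risk within an arm, none of which the documents give. The change is worth making before analysis. It adds to the totals and does not replace them.

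**What to change.** In sections 4.2 and 17.1, keep adverse event totals per arm as the burden measure and add beside them:

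1. Total VR sessions and total VR hours per arm, from the logged dates and times. Confirm that the log gives session duration in both arms; the dosage regression already needs hours for VICT.
2. Adverse events per session or per VR hour, with the VICT/control rate ratio and a 95% CI that allows for variation between children. Suitable choices are a negative binomial or Poisson model with log exposure as offset and child-level robust standard errors, or a child-level permutation test. A plain Poisson or exact conditional test should not be used, because it treats all sessions as independent.
3. Adverse events in the first training session by arm, as a descriptive comparison at equal exposure. It cannot carry a test: Fisher's exact test at 0.10 vs 0.20 with 15 per arm has about 4% power.

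The cost is SAP wording and a few table columns from data already kept; no study procedure changes. Two limits remain. The interval will be wide with few events. A per-session rate also does not correct for events unrelated to VR, which accrue by calendar day in long-stay inpatients.
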